### **Ordinal scales**

- a) The absolute value and change from baseline in the Ordinal scale from Day 1 through Day

29 will be summarized by treatment group and visit using descriptive statistics.

Mean change in Ordinal scales through Day 29 will be evaluated by fitting a linear mixed-effects model for repeated measures (MMRM). The model will include change from baseline in Ordinal scale as the repeated dependent variable; treatment (as a class variable), visit (as a class variable), and treatment-by-visit interaction as fixed effects; baseline Ordinal scale, age and gender as covariates; and measures within subject at each visit as a repeated measure. An unstructured covariance matrix will be used to model the within-subject error. If the fit of the unstructured covariance structure fails to converge, a compound symmetry covariance structure will be used. Parameters will be estimated using restricted maximum likelihood with the Kenward-Roger method for calculating the denominator degrees of freedom. Data collected starting at the Day 2 visit and up to the Day 29 visit will be included in this analysis. Missing data will not be imputed. From this model, the least-squares (LS) means and 95% CIs for each treatment group, the treatment difference in the LS means, the 95% CI for the difference, and the associated p-value will be reported on Days 15 and 29, as well as for the average across all post-baseline visits.

- b) The proportion of subjects in each severity category of the 7-point Ordinal scale at Day 15 and Day 29 will be tabulated. The difference in severity category distribution between treatment groups at Day 15 and Day 29 will be examined using proportional-odds cumulative logit model. The cumulative logits model will compare lower ordinal scales to higher ones, or equivalently, less favorable outcomes to more favorable ones. The model may be adjusted for baseline characteristics such as age and gender, if appropriate. The estimated odds ratio and 95% CI will be presented. Graphical illustrations of the fitted model will also be presented for Day 15 and Day 29.

The proportional odds assumption will be tested using a score test at the two-sided alpha level of 0.05. In the event that the proportional odds assumption is not satisfied, given the anti-conservative nature of the score test, the proportional odds model will still be used for the analysis, and the results will be presented along with the score test p-value to help put these results in context. If the proportion odds assumption is rejected or if the proportional odds model fails to converge, a sensitivity or alternative analysis using a non-parametric Wilcoxon Rank Sum test will be performed to estimate the median difference between the treatment groups.

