7.2.7 Day 29±1 day – All Subjects

Day 29±1 day may be performed at the study site or, if deemed appropriate, at an alternate site (e.g., subject's residence, local healthcare professional's site) under the care and supervision of trained healthcare personnel. If an in-person visit is unable to be conducted for Day 29, the study site will make a phone call to the subject to obtain as much information as possible remotely (e.g., Ordinal Scale, clinical features key symptoms, supplementation oxygen use, SAEs and TEAEs, concomitant medications).

Assessments include the following:

- Ordinal Scale assessment
- NEWS ([Appendix 2](#))
- Clinical features key symptoms: fever, cough, shortness of breath, fatigue, myalgia etc.
- Vital signs (temperature, systolic and diastolic blood pressure, pulse, respiratory rate)
- Record any supplemental oxygen administration (type, %, flow start/end date/time)
- Record details of mechanical ventilation parameters (start/end date/time)
- Record oxygen saturation (specify on or off oxygen supplementation)
- Record hospital discharge date
- Record ICU discharge date
- Assessment of ARDS (Berlin Criteria) ([Appendix 3](#))
- SOFA score ([Appendix 4](#))

GRIFOLS	Number	BLG-CL-PRT-000020	Version	4.0	Status	Effective	19-Jul-2021
	GC2007 - A Multicenter, Randomized, Open-label Parallel Group Pilot Study to Evaluate Safety and Efficacy of High Dose Intravenous Immune Globulin (IVIG) plus Standard Medical Treatment (SMT) versus SMT alone in Bioscience Industrial Group					Page	54 of 91

- Respiratory sample for quantitative measurement of SARS-CoV-2 viral load by NAT or PCR (real-time RT-PCR) (obtained via nasopharyngeal swab)
- Sample for quantitative measurement of IgM and IgG antibodies to SARS-CoV-2 (store serum samples frozen at -70°C for later analysis at an external lab)
- Serum Chemistry (creatinine, albumin, ALT, total bilirubin, LDH)
- Ferritin (serum), D-dimer (plasma, sodium citrate tube), CRP (serum)
- Hematology: absolute lymphocyte count and standard hematology (hemoglobin, hematocrit, platelet count, leukocyte count with differential)
- DAT
- Cytokine panel (IL-1 β , IL-10, IL-6, IL-8, IL-2, interferon γ , and TNF- α). Note: serum samples must be stored at -70°C for later analysis at a reference laboratory.
- Record SAEs and TEAEs
- Record standard care concomitant medications

7.2.8 Day 60 \pm 2 days and Day 90 \pm 2 days Phone Checks – All Subjects

Phone Checks will be performed on Day 60 and Day 90:

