## 1. INTRODUCTION

This statistical analysis plan (SAP) is based on the Protocol # GC2007 Version 3.0, dated 30 October, 2020, and titled “A Multicenter, Randomized, Open-label Parallel Group Pilot Study to Evaluate Safety and Efficacy of High Dose Intravenous Immune Globulin (IVIG) plus Standard Medical Treatment (SMT) versus SMT alone in Subjects with COVID-19 Requiring Admission to the Intensive Care Unit.” See the study protocol for full details.

This document details the statistical methods planned to perform the interim and final analyses of the study.

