All subjects will be followed daily through Day 10. After Day 10, if subjects are discharged from the hospital, evaluations at Day 15 and 29 are required. Berlin criteria for ARDS and SOFA score will be assessed on Day 1, 5, 15, and 29. Subjects remaining hospitalized will be followed daily through Day 29. Phone Checks will occur at Day 60 and Day 90 for vital status (living or deceased), any hospital re-admissions or serious/non-serious AEs after the Day 29 Final Clinic Visit. See Appendix A for the Schedule of Events.

Clinical trial finalization will coincide with the last study visit of the last subject enrolled in the clinical trial. For an individual subject, end of study for the purposes of determining disposition and successful study completion is the Day 29/Final Clinic Visit performed at the scheduled on-study timeframe.

An overview of the study design is presented below:

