#### **4.3 Assessment Windows**

Data will be summarized by nominal study visit recorded in the database.

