### **Assessment of clinical severity**

The NEWS will be calculated based on 7 clinical parameters and recorded on the eCRF. The absolute value and change from baseline in the total score from Day 1 through Day 29 will be summarized by treatment group and visit using descriptive statistics.

Change in NEWS total score through Day 29 will be evaluated by fitting a linear MMRM. The model will include change from baseline in NEWS total score as the repeated dependent variable; treatment (as a class variable), visit (as a class variable), and treatment-by-visit interaction as fixed effects; baseline NEWS total score, age and gender as covariates; and measures within subject at each visit as a repeated measure. An unstructured covariance matrix will be used to model the within-subject error. If the fit of the unstructured covariance structure fails to converge, a compound symmetry covariance structure will be used. Parameters will be estimated using restricted maximum likelihood with the Kenward-Roger method for calculating the denominator degrees of freedom. Data collected starting at the Day 2 visit and up to the Day 29 visit will be included in this analysis. Missing data will not be imputed. From this model, the least-squares (LS) means and 95% CIs for each treatment group, the treatment difference in the LS means, the 95% CI for the difference, and the associated p-value will be reported on Days 15 and 29, as well as for the average across all post-baseline visits.

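### The daily Ordinal and NEWS models fall back only to compound symmetry with Kenward-Roger inference, so Day 15 and Day 29 p-values can be too small

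*SAP*

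**What the plan says.** SAP 6.2, Ordinal scales (a), models change from baseline with visit as a class variable, treatment, treatment-by-visit, baseline score, age and gender. On which visits enter: "Data collected starting at the Day 2 visit and up to the Day 29 visit will be included in this analysis". The first covariance choice is unstructured. On failure: "If the fit of the unstructured covariance structure fails to converge, a compound symmetry covariance structure will be used". Estimation is by restricted maximum likelihood with Kenward-Roger denominator degrees of freedom. Differences, 95% CIs and p-values are reported for Days 15 and 29 and for the average over visits. No intermediate structure and no empirical variance is named.

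Assessment of clinical severity (NEWS) has the same specification. Assessment of SOFA score has the same fallback sentence but only three visits (Days 5, 15 and 29).

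On the visit schedule, SAP 3.1 says: "After Day 10, if subjects are discharged from the hospital, evaluations at Day 15 and 29 are required". Protocol 7.2.4 and 7.2.6 limit the daily assessments on Days 11-14 and 16-28 to subjects still in hospital. All three models also carry the rule "Missing data will not be imputed".

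**The concern.** The unstructured matrix asks a great deal of about 100 subjects, and late in-hospital days will be thinly filled. The fallback therefore has a fair chance of becoming the reported analysis.

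Compound symmetry is a strong assumption for patients who start in a similar state and then diverge to death, ventilation or home. If change from baseline is less variable in the first days than on Day 29, a pooled variance dominated by early days understates the Day 29 standard error. Kenward-Roger allows for having estimated the covariance parameters. It does not repair a wrong structure.

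At stake are the secondary Day 15 and Day 29 comparisons on Ordinal and NEWS, which could show an apparent effect that is not there.

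**Working it through.** **Inputs from the documents.** About 100 subjects randomized 1:1 (SAP 3.1, 9); two-sided 5% tests (SAP 4); 28 visits for Ordinal and NEWS, 3 for SOFA (SAP 6.2). Neither document gives variances, event rates or a power calculation, so there is no planned figure to reproduce, and every clinical course below is an assumption.

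**Covariance parameters**, k(k+1)/2:
- Ordinal and NEWS: 28 × 29 / 2 = 406
- SOFA: 3 × 4 / 2 = 6

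**Is failure plausible?** Two proxies, neither identical to non-convergence:
- Fewer than 30 scores on Day 28 (27 other visits + 2 arm means + 1) is one route to an unusable fit. Three assumed courses had 21%, 22% and 26% in hospital on Day 28 and 23-30% dead by Day 29. With scores stopping at death, the count fell below 30 in 97%, 95% and 78% of trials.
- In a separately programmed course with 30% deaths, about 22 subjects had a Day 28 NEWS value. The pairwise covariance matrix was not positive definite in 300 of 300 datasets.

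**Null simulations of the fallback.** 50 per arm, REML compound symmetry with the SAP's fixed effects, t reference with 95 or 97 df (Kenward-Roger itself was not coded). Set 1 has 800 trials per course; except in the carried-forward row, its results are for trials with fewer than 30 Day 28 scores (n = 774, 760, 623). Set 2 has 4,000 trials per course, with 21%, 30% and 38% deaths. Entries are type I error in %.

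| Setting | Day 15 | Day 29 | Day 29, sandwich |
|---|---|---|---|
| Set 1 Ordinal, scores stop at death | 14.2, 13.8, 17.0 | 13.4, 17.2, 18.5 | 5.0, 4.7, 5.6 |
| Set 1 Ordinal, death carried forward | not run | 19.4, 21.5, 21.4 | 4.4-4.6 |
| Set 1 NEWS | 6.5, 8.9, 8.5 | 5.3, 6.2, 8.7 | 4.5, 4.6, 4.5 |
| Set 2 Ordinal, death scored once | 15.0, 15.9, 16.3 | 19.9, 19.0, 18.0 | 4.7, 4.8, 5.0 |
| Set 2 Ordinal, death carried forward | 13.0, 13.5, 13.6 | 22.8, 23.6, 23.2 | 4.6, 4.6, 4.6 |
| Set 2 NEWS | 10.6, 11.2, 11.0 | 11.2, 10.1, 9.5 | 5.0, 5.0, 5.1 |

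A third run (400 trials, 17% deaths) gave Day 29 error of 18-21% for Ordinal and 12% for NEWS, against 4-6% with sandwich errors.

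**Is misspecification the cause?**
- Compound symmetry true: Day 29 error 3.9-5.8% (set 1) and 4.3% (set 2).
- AR(1) with correlation 0.95, constant variance, complete data: 4.8% on Day 15, 4.9% on Day 29.
- Variance rising from 0.5 to 3.0, complete data: 4.6% and 12.8%.
- The same, with half the subjects seen only on Days 15 and 29 after Day 10: 7.0% and 16.3%.
- AR(1) with correlation 0.9 under set 1's missingness, Day 29: 6-9% with constant SD, 11-14% if the SD grows 1.5-fold, 19% if it doubles; sandwich 3-6%.

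**Arithmetic check.** True alpha ≈ 2[1 − Φ(1.96 r)], with r = model SE / true SD. For set 1 Ordinal on Day 29 (first table row):
- 0.256/0.348 = 0.736, giving 14.9% (simulated 13.4%)
- 0.266/0.377 = 0.706, giving 16.7% (simulated 17.2%)
- 0.262/0.395 = 0.663, giving 19.4% (simulated 18.5%)

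The understated standard error accounts for the excess.

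**The case against.** **The trigger is unproven.** The SAP's condition is non-convergence, and its probability cannot be computed from the documents. If death is carried forward as category 1, fewer than 30 Day 28 Ordinal scores occurs in 0.1% of trials or fewer, so that route to failure almost disappears for Ordinal. This stands, and it is why failure is called likely and not certain. The 406 parameters remain, and if the fit fails anyway, the fallback's error with death carried forward is 19-24%.

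**NEWS is weaker evidence.** Two of the three set 1 Day 29 results (5.3%, 6.2%) lie within about 1.5 simulation standard errors of 5%. The other runs are higher, but the size depends on assumed trajectories. This also stands.

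**There are other analyses.** For Ordinal (b) the SAP says: "The difference in severity category distribution between treatment groups at Day 15 and Day 29 will be examined using proportional-odds cumulative logit model". It adds a Wilcoxon analysis if proportionality is rejected or the model fails to converge. Neither uses a repeated-measures covariance. NEWS also has a time-to-response log-rank test. All these endpoints are secondary, in a pilot without multiplicity adjustment. This limits the harm but does not correct the mixed-model p-values.

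**Stronger readings the documents do not support:**
- A reader might infer that the NEWS and SOFA models describe survivors only. They do not: a likelihood model without imputation extrapolates past death under missing-at-random. With assumed deaths of 25% and 16%, survivor means on Day 29 were -4.02 and -3.69. A three-visit unstructured fit gave -3.51 and -3.38, close to the no-death means of -3.52 and -3.38.
- A reader might infer that living subjects without a score, for example after a phone visit, have no rule. The no-imputation sentence is the rule for these models.
- A reader might infer that earlier deaths drop out of the proportional-odds analysis. Category 1 is death, so an analyst would naturally score them 1.

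**Conclusion.** The concern holds for the daily Ordinal and NEWS mixed models, conditional on the unstructured fit failing. If it fails and the variance of change grows over follow-up, nominal 5% tests on Day 29 run at about 13-24% for Ordinal and 5-12% for NEWS. Day 15 gives about 13-17% and 7-11%. Sandwich errors bring the level to 3-6%.

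These sizes rest on assumed clinical courses. When compound symmetry is true, or when variance is constant and data are complete, the level stays near 5%. The finding is firmer for Ordinal than for NEWS. The six-parameter SOFA model should rarely need the fallback, and the primary mortality test is untouched. It is worth fixing because the stated rule can give a wrong answer and the cure is text only.

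**What to change.** In SAP 6.2, Ordinal scales (a) and Assessment of clinical severity, state that if the unstructured fit does not converge or is not positive definite, the fallback model will be reported with small-sample-corrected by-subject sandwich standard errors (for example Mancl-DeRouen) and between-subject degrees of freedom, in place of Kenward-Roger. The working structure can be compound symmetry, heterogeneous Toeplitz (28 + 27 = 55 parameters) or heterogeneous AR(1) (28 + 1 = 29). A richer structure alone is not enough: in a separate run of 300 trials under other settings, heterogeneous AR(1) with model-based errors still gave 12.3-12.7% for Ordinal.

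Two minor clarifications: say that Ordinal category 1 is carried forward from death through Day 29, and that the NEWS and SOFA models extrapolate past death under missing-at-random. Do not label them as describing survivors. No further supplementary analysis is needed on this account.

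The cost is SAP text and programming, with no change to endpoints or visits. Intervals widen. For Ordinal on Day 29, sandwich over model SE in set 1 is 0.351/0.256 = 1.37, 0.380/0.266 = 1.43 and 0.397/0.262 = 1.52, so 37-52% wider. For NEWS the widening was 4-13% in set 1. In set 2, model SE over true SD was 0.81-0.84, implying about 19-23% (1/0.84 to 1/0.81). Sandwich errors correct the standard error, not the missing-data assumption.

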All subjects will be followed daily through Day 10. After Day 10, if subjects are discharged from the hospital, evaluations at Day 15 and 29 are required. Berlin criteria for ARDS ([Appendix 3](#)) and SOFA score ([Appendix 4](#)) will be assessed on Day 1, 5, 15, and 29. Subjects remaining hospitalized will be followed daily through Day 29. Days 15±1 and 29±1 may be performed at the study site or, if deemed appropriate, at an alternate site (e.g., subject's residence, local healthcare professional's site) under the care and supervision of trained healthcare personnel. If an in-person visit is unable to be conducted for Day 15 or

GRIFOLS Bioscience Industrial Group	Number	BLG-CL-PR7-000020	Version	4.0	Status	Effective	Effective Date	19-Jul-2021
	GC2007 - A Multicenter, Randomized, Open-label Parallel Group Pilot Study to Evaluate Safety and Efficacy of High Dose Intravenous Immune Globulin (IVIG) plus Standard Medical Treatment (SMT) versus SMT alone in						Page	34 of 91

Day 29, the study site will make a phone call to the subject to obtain as much information as possible remotely (e.g., Ordinal Scale, clinical features key symptoms, supplementation oxygen use, SAEs and TEAEs, concomitant medications). Phone Checks will occur at Day 60 and Day 90 for vital status (living or deceased), any hospital re-admissions or serious/non-serious adverse events after the Day 29 Final Clinic Visit. Details are provided in [Appendix 1](#) (Schedule of Study Procedures). Clinical status will be evaluated for all hospitalized subjects daily with vital signs, Ordinal Scale (7 categories analogous to Cao et al. 2020), and NEWS at Screening/Baseline and during IVIG plus SMT or SMT alone treatment and during Follow-up. The NEWS calculation is delineated in [Appendix 2](#) and can be calculated using the on-line web tool at <https://www.mdcalc.com/national-early-warning-score-news> .

For subjects in the combination arm (IVIG plus SMT) all laboratory samples must be drawn prior to infusion of IVIG, if laboratory assessments are required for a day in which IVIG is being infused.

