Appendix 1 Schedule of Study Procedures

Study Period	Screen/ Baseline	1 st IP	SMT and Daily Evaluations										Follow- Up	Follow-Up Clinic Visit Day			Phone Checks	
			2	3	4	5±1 day	6	7	8	9	10	11-14 Daily if in hospital		15±1 e day	16-28 Daily if in hospital	29 ^{e,f} ± 1 day	Day 60 ± 2 days	Day 90 ± 2 days
Study Day	1																	
Procedures/assessments																		
Informed consent	X																	
Inclusion/exclusion criteria	X																	
Demography (age [year of birth], age at screening [years], gender [if female, fertility status], race, and ethnicity), disease characteristics (date of exposure, date of onset ^a)	X																	
Pregnancy test ^b	X																	
Ordinal Scale (at the 1st assessment of a given day) ^c	X		X	X	X	X	X	X	X	X	X	X	X	X	X	X	X	
National Early Warning Score (NEWS) Appendix 2	X		X	X	X	X	X	X	X	X	X	X	X	X	X	X	X	
Clinical features key symptoms: fever, cough, shortness of breath, fatigue, myalgia etc.	X		X	X	X	X	X	X	X	X	X	X	X	X	X	X	X	
Vital signs (temperature, systolic and diastolic blood pressure, pulse, respiratory rate)	X	X ^k	X ^k	X ^k	X ^k	X ^k	X ^k	X	X	X	X	X	X	X	X	X	X	
Initial Body Weight for determining all IVIG doses if randomized to combination arm	X																	
Body weight for assessing fluid balance twice daily (at least 8 hours)		X	X	X	X	X	X											

Study Period	Screen/ Baseline	1 st IP	SMT and Daily Evaluations										Follow- Up	Follow-Up Clinic Visit Day			Phone Checks	
			2	3	4	5±1 day	6	7	8	9	10	11-14 Daily if in hospital		15±1 e day	16-28 Daily if in hospital	29 ^{e,f} ± 1 day	Day 60 ± 2 days	Day 90 ± 2 days
Study Day	1																	
Procedures/assessments																		
should separate the time from the first recorded weight)																		
Record result of historical SARS-CoV-2 PCR (qualitative RT-PCR) or other FDA-approved or regulatory-authority-approved diagnostic assay in any specimen during the current hospital admission prior to randomization (eligibility criterion)	X																	
Record any supplemental oxygen administration (type, %, flow start/end date/time)	X		X	X	X	X	X	X	X	X	X	X	X	X	X	X	X	
Record any mechanical ventilation (start/end date/time)	X		X	X	X	X	X	X	X	X	X	X	X	X	X	X	X	
Record oxygen saturation (specify on or off oxygen supplementation)	X		X	X	X	X	X	X	X	X	X	X	X	X	X	X	X	
Randomization (after all Screen/Baseline assessments complete)	X																	

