## 3.2 Treatment

### 3.2.1 Randomization Scheme and Treatment Arm Assignment

Subjects will be randomized 1:1 to receive either combination treatment with Gamunex-C plus SMT or SMT alone. A central randomization will be used for this study. A randomization list containing the randomization numbers and the corresponding randomized treatment assignments will be generated and be stored in a secured area that is only accessible to the randomization team.

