## 4. GENERAL CONSIDERATIONS FOR DATA ANALYSIS

Unless otherwise specified, continuous variables will be summarized using descriptive statistics (n, mean, standard deviation, median, minimum, and maximum). Categorical variables will be summarized showing the number and percentage of subjects within each category.

Summary results will be provided for each treatment group. All tabulations will be based on pooled data across centers.

All statistical tests will be two-sided and tested at the 5% level of significance.

Analyses will be performed using SAS for Windows statistical software, version 9.4 or higher (SAS, Cary, NC), except where other software may be deemed more appropriate. In the event that other software is used to perform some analyses, the details will be provided in the Clinical Study Report.

■ will perform all efficacy and safety analyses described in this SAP.

Subject data will be listed, sorted by treatment group and subject number. When applicable, listings will be additionally sorted by visit and assessment date/time.

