### **9. SAMPLE SIZE AND POWER CALCULATIONS**

Because of the urgency and lack of previous prospective COVID-19 data, sample size estimation remains incompletely defined; however the size of this pilot study is commensurate with other Phase 2 investigations ongoing during the COVID-19 pandemic. Approximately 100 subjects are allowed to be randomized as part of a humanitarian effort against COVID-19.

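### The Ordinal-scale MMRM has no rule for days after death or unrated days after discharge, so its contrasts can be distorted if mortality differs between arms

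*SAP*

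**What the plan says.** **Scale.** In SAP 2.2.2 category 1 is death, 2 to 5 are levels of care in hospital, and 6 and 7 are out of hospital with and without activity limitation.

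**Schedule.** Protocol Appendix 1 lists the item as "Ordinal Scale (at the 1st assessment of a given day". It is rated daily for everyone through Day 10, on Days 11-14 and 16-28 only while in hospital, and on Days 15 and 29 for all. Protocol 4.2 confirms this: "After Day 10, if subjects are discharged from the hospital, evaluations at Day 15 and 29 are required". Protocol 5.3.2 names death among the reasons for withdrawal.

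**Analysis (a).** SAP 6.2 models change from baseline on the ratings collected from Day 2 to Day 29. The covariance is unstructured, with compound symmetry if that fit does not converge. Results are reported for Day 15, Day 29 and the average over all post-baseline visits. The missing-data rule is "Missing data will not be imputed". SAP 4.3 adds: "Data will be summarized by nominal study visit recorded in the database". SAP 4.4 promises worst-case handling for selected efficacy endpoints, with details in Section 6, but the Ordinal text there gives none.

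**Analysis (b).** All seven categories are tabulated at Days 15 and 29 and compared with a proportional-odds model. No missing-data sentence is attached.

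**Contrast.** For ICU, ventilation, hospital and oxygen days, SAP 6.2 does give deceased subjects a value through Day 29 (for ventilation and oxygen, when no stop date is recorded).

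**The concern.** On SOFA or NEWS a dead subject has no value. On this scale death is a value, the worst one, and its date is known. Yet the model text uses only collected ratings, and no sentence creates a rating after death. Because the rating is taken at the first assessment of the day, a subject who dies later that day may never be rated 1 at all. Discharged subjects, who sit at the good end of the scale, are unrated on most days after Day 10.

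The model then estimates what a deceased subject would have scored from that subject's earlier ratings in hospital. If one arm has fewer deaths, it keeps more very sick survivors on the scale, while the other arm's deaths disappear from it. The comparison could then understate a benefit or even reverse it. Two programmers could also build different datasets from the same paragraph.

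**Working it through.** **1. Days affected.** The model has 28 visits (Days 2-29). Days without a rating after live discharge are Days 11-14 (4) and 16-28 (13): 4 + 13 = 17 of 28. On a literal reading, a subject who dies on Day 8 loses Days 9-29, which is 21 of 28.

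**2. Likely covariance.** An unstructured matrix over 28 visits has 28 x 29 / 2 = 406 parameters. The plan has about 100 subjects: "Approximately 100 subjects are allowed to be randomized as part of a humanitarian effort against COVID-19". The compound-symmetry fallback is therefore likely.

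**3. Inputs for size.** There is no plan figure to reproduce. On assumptions the SAP says "Because of the urgency and lack of previous prospective COVID-19 data, sample size estimation remains incompletely defined", and the documents give no ICU mortality rate. The following were therefore assumed: baseline categories 2/3/4 at 40/45/15%; a daily seven-state transition model with between-subject frailty; control Day 29 mortality of 27.5% to 48%; five benefit patterns and a null. There were 15,000 subjects per arm for compound symmetry and 4,000 per arm for unstructured. The model had visit, treatment-by-visit and baseline score; age and gender were left out. A positive difference favours IVIG.

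**4. Compound symmetry.** *Filled* scores the dead 1 every day and rates the discharged daily. *As recorded* rates death once, on the day of death, and leaves the discharge gaps. *Scored at 15/29* also scores the dead 1 on those two days. Change = (value - filled) / filled; for example, combined mid at Day 29 is (0.425 - 0.737) / 0.737 = -42%.

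| Benefit pattern (Day 29 mortality, SMT vs IVIG) | Day 29 filled | Day 29 as recorded | Average filled | Average as recorded | Average, scored at 15/29 |
|---|---|---|---|---|---|
| None (38.4% vs 37.9%) | 0.022 | 0.015 | 0.003 | 0.004 | 0.009 |
| Combined, low (27.5% vs 17.5%) | 0.706 | 0.466 (-34%) | 0.476 | 0.329 (-31%) | 0.351 (-26%) |
| Combined, mid (38.8% vs 26.9%) | 0.737 | 0.425 (-42%) | 0.511 | 0.343 (-33%) | 0.374 (-27%) |
| Combined, high (48.0% vs 36.3%) | 0.678 | 0.337 (-50%) | 0.478 | 0.290 (-39%) | 0.327 (-32%) |
| Recovery only (39.2% vs 33.0%) | 0.599 | 0.522 (-13%) | 0.453 | 0.349 (-23%) | 0.340 (-25%) |
| Deaths only (38.8% vs 28.7%) | 0.250 | -0.110 (sign reversed) | 0.156 | 0.003 (-98%) | 0.058 (-63%) |

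Between 39% and 54% of subject-visits are lost. When the dead are scored 1 at Days 15 and 29, both of those contrasts agree with the filled data to within 0.003.

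**5. Unstructured.** With death rated once, the change is -14% to +11% at Day 29, +4% to +19% at Day 15 and -3% to +10% for the average. If death is never rated, Day 29 falls from 0.711 to 0.439 in the mid pattern (-38%) and from 0.300 to -0.009 in the deaths-only pattern. If the dead are scored at Days 15 and 29, the average falls by 1% to 8%.

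**6. Source of the loss (compound symmetry, mid).** Dropping post-death days moves Day 29 from 0.74 to 0.45; adding the discharge gaps takes it to 0.43. For the average the steps are 0.51, 0.38 and 0.34. Missing deaths drive Day 29; the discharge gaps mainly touch the average.

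**7. Cross-check.** A separate small simulation used 50 per arm, control mortality of about 24%, compound symmetry and 60 replicates. Day 29 fell from 0.65 to 0.36-0.40 under a combined benefit, and went from +0.15 to between -0.14 and -0.18 under a mortality-only benefit.

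**The case against.** A reader might infer that the SAP forbids scoring the dead. It does not go that far. The no-imputation sentence sits in part (a) only and recurs as standard wording for SOFA and NEWS. Giving a known death category 1 applies the scale's definition and fills in nothing unknown. Part (b) tabulates a death category at Days 15 and 29, which makes sense only if the dead count as 1 there. Protocol 7.2.5 and 7.2.7 are headed as applying to all subjects, and the eCRF completion rules are not available to us. This part of the objection stands: the SAP is silent on scoring death, and on the reading that part (b) implies, the Day 15 and Day 29 contrasts are sound.

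The large figures also need the fallback covariance, and discharge does not settle 6 versus 7, because activity limitation is not rated on non-visit days. Both points stand.

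The objection does not remove the need for a rule. Nothing in part (a) adopts part (b)'s implied scoring. Even if it is adopted, the reported all-visit average still shrinks by 25% to 63% under the likely fallback. The unstructured matrix protects the result only if every death is rated at least once, which first-assessment scoring does not ensure.

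**Conclusion.** The concern holds in a conditional form. Followed literally, SAP 6.2 (a) drops post-death days and discharged non-visit days from a scale on which death is a category. If mortality differs between arms, the all-visit average can be materially distorted, and so can Days 15 and 29 if the dead are omitted there. In the assumed combined-benefit settings under compound symmetry, with death rated once, the Day 29 loss is 34% to 50%.

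Two stronger readings are tempting, and the material does not support them. One is that the treatment effect is biased whatever happens: with no difference between arms every contrast stayed within about 0.02 of the filled data, and under an unstructured matrix with death rated once the shifts were small and of either sign. The other is that a mortality benefit would generally show as harm: with death rated once, the reversal appeared only with compound symmetry, a benefit confined to death, and the dead unscored at Day 29.

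All sizes rest on assumed event and transition rates. This is a secondary endpoint in an exploratory pilot. The primary mortality analysis has its own rule for missing vital status and is not affected. The change should be made before database lock.

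**What to change.** In SAP 6.2, Ordinal scales:

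- **(a) and (b):** assign category 1 from the date of death through Day 29, including Days 15 and 29, whatever the first assessment on the day of death showed. State that this applies the scale's definition and is not imputation.
- **(a) only:** for subjects known to be alive and out of hospital, assign category 6 on non-visit days, and repeat the analysis with 7 as a sensitivity analysis.
- Do not carry a category back from a later visit. A subject readmitted or dead by Day 29 would otherwise receive a hospitalised or death score on days spent alive at home.
- Leave a day missing where hospital status is unknown.

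The cost is SAP wording plus one derivation from death and discharge dates already collected. There are two small downsides. Category 6 versus 7 is assumed on non-visit days. Readmissions before Day 29 must be taken from admission or SAE records, because the schedule asks about readmission explicitly only at the Day 60 and Day 90 calls.
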